#### 1.2.3 Residual Effect Period

The REP of ethinylestradiol is 5 days based on a minimum observation period of at least 5-fold estimated  $t\frac{1}{2}$  (i.e. 5 x 20 h, or 4.2 days, rounded to 5 days). The REP of drospirenone is 6 days based on a minimum observation period of at least 5-fold estimated  $t\frac{1}{2}$  (i.e. 5 x 40 h, or 8.3 days, rounded up to 9 days).

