**Trial Protocol** 

Page 21 of 84

Table 1.4.2: 1 Overview of trial-related risks for this trial (cont.)

Possible or known risks of clinical relevance	Summary of data, rationale for the risk	Mitigation strategy
Inve	estigational Medicinal Product: BI	1358894
In	vestigational Medicinal Product: Y	
Increased risk of venous and arterial thromboembolism	The incidence of venous thromboembolic events is 2 per 10000 women in one year, if no hormonal contraceptives are used. The incidence is increased to 9 - 12 per 10000 women after intake of COC containing drospirenone [R23-0484].  The risk of venous thromboembolism increases in the presence of pre-existing risk factors such as obesity, immobilization, family history of thromboembolism, hypercoagulability states and increased age.  Epidemiologic studies showed that the use of COC increases the risk of arterial thromboembolism (myocardial infarct) and cerebrovascular events (transient ischaemic attack, stroke). The risk increases when there are pre-existing conditions such as older age, smoking, arterial hypertension, obesity, family history, migraine, prothesis valves, atrial fibrillation, dyslipidaemia, lupus) [R23-0484]	- Close monitoring of adverse events, safety lab, ECG and vital signs - Subjects with additional risk factors will not be allowed in participation in the trial - Subjects with a recent history of malignancy within 5 years (except appropriately treated basal cell carcinoma of the skin) will be excluded from participation - In case of occurrence of a serious side effect, trial treatment to be discontinued, and diagnostics and treatment have to be initiated according to local standard of care - In addition to the general inclusion examination, the suitability of subjects for taking this oral contraceptive will be assessed by a gynaecologist prior to trial entry

c41232811-04 Trial Protocol Page 22 of 84

Table 1.4.2: 1 Overview of trial-related risks for this trial (cont.)

Possible or known risks of clinical relevance	Summary of data, rationale for the risk	Mitigation strategy		
Investigational Medicinal Product: Yasmin®				

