2.2.2.3 Safety and tolerability

Safety and tolerability of BI 1358894 will be assessed based on:

- Adverse events (including clinically relevant findings from the physical examination)
- Safety laboratory tests
- 12-lead ECG
- Vital signs (blood pressure, pulse rate)
- Suicidality assessment (C-SSRS)

Proprietary confidential information © 2023 Boehringer Ingelheim International GmbH or one or more of its affiliated companies

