c41232811-04 Trial Protocol

Page 44 of 84

Proprietary confidential information © 2023 Boehringer Ingelheim International GmbH or one or more of its affiliated companies

Table 5.2.3: 1 Routine laboratory tests (cont.)

Functional lab group	BI test name [comment/abbreviation]	A	В	С
Substrates	Glucose (Plasma)	X	X	X
	Creatinine	X	X	X
	GFR/ CKD-EPI	X		
	Bilirubin, Total	X	X	X
	Bilirubin, Direct	X	X	X
	Protein, Total	X	X	X
	C-Reactive Protein (Quant)	X	X	X
	Uric Acid	X		
	Cholesterol, total	X		
	Cholesterol, HDL	X		
	Cholesterol, LDL	X		
	Triglyceride	X		
Electrolytes	Sodium	X	X	X
	Potassium	X	X	X
Urinalysis (Stix)	Urine Nitrite (qual)	X		X
	Urine Protein (qual)	X		X
	Urine Glucose (qual)	X		X
	Urine Ketone (qual)	X		X
	Urobilinogen (qual)	X		X
	Urine Bilirubin (qual)	X		X
	Urine HGB (qual)	X		X
	Urine leukocyte esterase (qual)	X		X
	Urine pH	X		X
Urine sediment	Only positive findings will be reported (for instance, the			
(microscopic	presence of sediment bacteria, casts in sediment, squamous			
examination if	epithelial cells, erythrocytes, leukocytes)			
erythrocytes,				
leukocytes nitrite or				
protein are abnormal				
in urine)				

A: parameters to be determined at Visit 1 (screening examination)

B: parameters to be determined on Day 1 of each period (for time points refer to Flow Chart)

C: parameters to be determined at Visit 5 (end of trial examination)

The tests listed in Table 5.2.3: 2 are exclusionary laboratory tests that may be repeated as required. The results will not be entered in the CRF/database and will not be reported in the CTR. Except for pregnancy tests and drug screening, it is planned to perform these tests during screening only. Pregnancy testing will be performed at screening, prior to run-in, prior to each treatment period, and as part of the end of trial examination. Drug screening will be performed at screening and on day 20 of each treatment period.

Boehringer Ingelheim BI Trial No.: 1402-0019

Proprietary confidential information © 2023 Boehringer Ingelheim International GmbH or one or more of its affiliated companies

Table 5.2.3: 2 Exclusionary laboratory tests

Functional lab group	Test name
Drug screening (urine)	Amphetamine/MDA
	Barbiturates
	Benzodiazepine
	THC
	Cocaine
	Methadone
	Methamphetamines/MDMA/Ecstasy
	Morphine (MOP)
	Phencyclidine
	Tricyclic antidepressants
Cotinine test (urine)	Cotinine (metabolite of nicotine) in urine
Infectious serology (blood)	Hepatitis B surface antigen (qualitative)

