### 7.2.5 Safety analyses

Safety will be analysed based on the assessments described in Section 2.2.2.3. All treated subjects (TS, refer to Section 7.2) will be included in the safety analysis. Safety analyses will be descriptive in nature and based on BI standards. No hypothesis testing is planned.

Boehringer Ingelheim BI Trial No.: 1402-0019

c41232811-04 Trial Protocol Page 61 of 84

19 Oct 2023

Proprietary confidential information © 2023 Boehringer Ingelheim International GmbH or one or more of its affiliated companies

For all analyses, the treatment actually administered (= treatment at onset) to the subject will be used (any deviations from the assigned treatment will be discussed in the minutes of the Report Planning Meeting).

Treatments will be compared in a descriptive way. Tabulations of frequencies/proportions will be used to evaluate categorical (qualitative) data, and tabulations of descriptive statistics will be used to analyse continuous (quantitative) data.

Measurements (such as ECG, vital signs, or laboratory parameters) or AEs will be assigned to treatments (see Section 4.1) based on the actual treatment at the time of the measurement or on the recorded time of AE onset (concept of treatment emergent AEs). Therefore, measurements performed or AEs recorded prior to first intake of trial medication will be assigned to the screening period. Those occurring in the run-in period will be assigned to the run-in period, while all others -from first trial medication intake in respective treatment period to end of REP (see Section 1.2.3) will be assigned to the respective treatment period. Events occurring after the REP but prior to end of study examination date will be assigned to follow-up'. In case of two or more treatments, the follow-up will be summarized according to the previous treatment. These assignments including the corresponding time intervals will be defined in detail in the TSAP. Note that AEs occurring after the last per protocol contact but entered before final database lock will be reported to Pharmacovigilance only and will not be captured in the trial database.

Additionally, further treatment intervals (analysing treatments) may be defined in the TSAP in order to provide summary statistics for time intervals, such as combined treatments, ontreatment totals, or periods without treatment effects (such as screening and follow-up intervals).

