Overall, the REP of 17 days will be considered for evaluation of adverse events in the trial.

The study was prematurely terminated after run-in period. Therefore, the subjects received combined oral contraceptives (COC), but none of the subjects was treated with BI 1358894. Consequently, the REP of ethinylestradiol and drospirenone was 9 days.

Based on this, the following study phases will be defined for the analysis of AEs:

- **Screening**
 - Ranging from 0:00h on day of informed consent until time of first administration of COC.
- **On treatment (labelled “COC (run-in)”)**
 - Ranging from the time of first administration of COC until last administration of COC plus 9 days (216 h) thereafter OR until trial termination (0:00 h on the day after trial termination), whatever occurs first.
- **Follow-up (labelled “Follow-up (run-in)”)**
 - Ranging from the end of REP until trial termination (0:00 h on the day after trial termination).

Section 7.2.5 of the CTP:

Note that AEs occurring after the last per protocol contact but entered before database lock will be reported to Pharmacovigilance only and will not be captured in the trial database.

The following AE displays will be provided in the report:

- In Section 15.3 and Appendix 16.1.13.1.8 (for ClinicalTrials.gov only) of the CTR displays, the on treatment phase will be analysed (labelled with the short label of the study treatment). The screening and follow-up phases will not be included in this analysis.
- In Section 15.4 and Appendix 16.2 (Listings) of the CTR displays, the screening period, as well as the follow-up phases will additionally be included and no totals will be provided.

For detailed information on the handling of the treatments refer to Technical TSAP ADS (analysis data set) plan and Analysis Data Reviewers guide.

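### No blood chemistry is scheduled at established exposure, so COC plus BI 1358894 has no scheduled on-treatment laboratory value

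*Protocol*

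**What the plan says.** Chemistry belongs to three panels in protocol Table 5.2.3: 1. Panel A is drawn at screening and Panel C at Visit 5 (EoS, Day 42-52 in the Flow Chart). The legend gives the panel in between as "B: parameters to be determined on Day 1 of each period (for time points refer to Flow Chart". The laboratory marks on Days 10 and 20 carry Flow Chart footnote 8, which covers urine tests only. The Day 22 row (504:00) of each period has a PK blood draw, ECG and vital signs, but no laboratory mark.

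Section 5.2.3 requires an 8 h fast before safety samples, and section 4.1.4 has breakfast eaten in full before dosing.

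Section 7.2.5 assigns a measurement to a treatment period from "first trial medication intake in respective treatment period to end of REP". For what comes later it says: "Events occurring after the REP but prior to end of study examination date will be assigned to follow-up".

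The purpose of the laboratory data is stated in several places:

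- Section 2.2.2.3 opens with "Safety and tolerability of BI 1358894 will be assessed based on" and lists safety laboratory tests.
- Section 5.7 says the scheduled measurements allow laboratory changes due to trial medication to be monitored.
- Section 7.2.5 plans an evaluation of laboratory differences from baseline.
- The only adverse event of special interest, potential severe drug-induced liver injury (5.2.6.1.4), and withdrawal criterion 5 (3.3.4.1) are defined by ALT, AST and bilirubin.

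**The concern.** A laboratory schedule meant to describe the safety of a drug should have at least one sample while the drug is present. Here the samples sit on either side of the 21 days of BI 1358894: one just before the first dose and one at least three weeks after the last. The COC is also sampled only after a tablet-free week.

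At stake is a symptom-free change, above all in liver enzymes, that arises under BI 1358894 and has resolved by EoS. No scheduled sample would show it, and none could trigger withdrawal criterion 5 during BI 1358894 dosing. The planned differences from baseline would contain no value under the test treatment.

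**Working it through.** **Inputs.** Half-lives: ethinylestradiol 10-20 h (protocol 1.2.2.1), drospirenone 30-40 h (1.2.2.2), BI 1358894 50-70 h (SAP 6.1). The 17-day residual effect period (REP) of BI 1358894 is also taken from SAP 6.1, because that text is blacked out in the protocol copy. Last COC doses: Day -8 of run-in and Day 21 of each period. EoS: Day 42-52 on the Period 2 clock.

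**1. The plan's own figures.** REP = 5 × half-life. Ethinylestradiol: 5 × 20 h = 100 h = 4.2 days, rounded to 5. Drospirenone: 5 × 40 h = 200 h = 8.3 days, matching "5 x 40 h, or 8.3 days, rounded up to 9 days". Both reproduce. The same drospirenone sentence in 1.2.3 also says 6 days. The SAP uses 9 ("last administration of COC plus 9 days (216 h) thereafter"). I carry both.

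**2. Panel B is pre-dose.** The sample must be fasted, and breakfast starts 30 minutes before dosing and is finished first. A compliant Day 1 sample therefore precedes the dose.

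**3. Exposure at Panel B.** From Day -8 to Period 1 Day 1, and from Period 1 Day 21 to Period 2 Day 1 (Day 29 on the Period 1 clock), is 8 days = 192 h. Share left = 2^-(gap / half-life):

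- drospirenone: 2^-(192/30) = 1.2% to 2^-(192/40) = 3.6%
- ethinylestradiol: at most 2^-(192/20) = 0.13%
- BI 1358894: none taken yet

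**4. Exposure at EoS.** 42 - 21 = 21 days (504 h) to 52 - 21 = 31 days (744 h). BI 1358894 left: at most 2^-(504/70) = 0.7%. Its REP ends on Day 21 + 17 = 38, so EoS comes 4-14 days later.

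**5. Scheduled chemistry values per completing subject, by 7.2.5 phase.**

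| Phase | 9-day drospirenone REP | 6-day drospirenone REP |
|---|---|---|
| Screening (Panel A) | 1 | 1 |
| Run-in (Period 1 Day 1) | 1 | 1 |
| Reference (Period 2 Day 1) | 1, off drug | 0 |
| Test | 0 | 0 |
| Follow-up after test (EoS) | 1 | 1 |

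With 9 days the reference window runs to Day 30 and includes Day 29. With 6 days it ends on Day 27 and does not. The zero for test does not depend on this choice: any REP shorter than 42 - 21 = 21 days gives it. The follow-up sentence is worded for events; I read it as covering measurements too.

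**6. With a Day 22 sample.** At 504:00, 24 h after the 21st daily dose, the share of steady state reached is 1 - 2^-(504/70) = 99.3% for BI 1358894 (half-life 70 h) and 1 - 2^-(504/40) = 99.98% for drospirenone (40 h).

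**The case against.** The strongest case for the schedule is that it brackets BI 1358894: Period 2 Day 1 and EoS would show any lasting change. Liver symptoms prompt unscheduled tests (5.2.6.1.4), subjects are questioned about adverse events throughout dosing, and discontinued subjects have the EoS examination early (3.3.4, 6.2.3). The BI 1358894 risk rows are blacked out and may hold a reason for the sampling frequency. Amendment 1 records several changes requested by the authorities, and on-treatment chemistry is not among them. All of this stands. It narrows the gap to silent changes that resolve before EoS in subjects who do not discontinue, but it does not supply a sample under exposure.

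The count itself can be challenged. Panel B is not labelled pre-dose, and section 6.1 allows ±30 min for laboratory tests. A sample just after the first dose would count for the test treatment in name, at almost no exposure. Section 7.2.5 leaves the detailed intervals to the SAP, which was written after termination and defines run-in phases only. It also summarises follow-up under the previous treatment, so EoS values could appear under test, but as follow-up.

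Two stronger readings are tempting, and the documents do not support them:

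- A reader might infer that a specific monitoring promise is broken, because Table 1.4.2: 1 lists "Close monitoring of adverse events, safety lab, ECG and vital signs". That row concerns thromboembolism, and Panel B contains no coagulation test. The mitigation given for hyperkalaemia is normal kidney function.
- A reader might infer that a planned test-versus-reference laboratory contrast cannot be made, from "Treatments will be compared in a descriptive way". That sentence covers safety data in general. The laboratory-specific plan is comparison with reference ranges and differences from baseline.

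**Conclusion.** The point holds for subjects who complete the schedule. The test treatment has zero scheduled on-treatment chemistry values. The reference has one nominal, off-drug value with the 9-day drospirenone REP and none with 6 days. This falls short of sections 2.2.2.3 and 5.7 and leaves the liver criteria without a scheduled trigger during BI 1358894 dosing.

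It rests on Panel B being pre-dose, on the half-lives and 17-day REP quoted above, and on 7.2.5 being applied as written. It is a gap in safety description, worth closing because closing it is cheap. It does not touch the pharmacokinetic objective. SAP section 4 states that no subject started Period 1, so no reported result changes. The documents do not show that liver injury in general would go unnoticed: symptomatic or lasting changes have a route to detection.

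**What to change.** Add Panel B at the existing 504:00 blood draw on Day 22, before breakfast. The fasting rule is met: dinner is at 492:00, 12 h earlier, and Flow Chart footnote 3 puts the meal last. Period 2 is the essential sample. Period 1 supplies the matched COC-alone value and falls 7 days before the first BI 1358894 dose. Amend the Flow Chart, and reword the legend so that Panel B is due on Day 1 (pre-dose) and on Day 22 (before breakfast) of each period. Leave EoS at Day 42-52, which the authorities requested.

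**Cost.** Up to two panels per subject (64 for 32 subjects), with no new visit or venipuncture. Blood volume from the stated tube sizes:

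- COC PK: 16 draws × 2 periods × 2 analytes × 2.7 mL = 172.8 mL
- BI 1358894 PK: 5 × 2.7 = 13.5 mL
- Hormones: 3 × 2 × 4.9 = 29.4 mL
- Sum: 215.7 mL

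The protocol gives no volume for a safety panel. Assuming 10-20 mL each, four panels now bring the total to 256-296 mL and six would bring it to 276-336 mL, below the 500 mL limit in 1.4.2.

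**Limit.** The Period 2 sample follows the last dose. It can detect a change and start liver follow-up, but it cannot stop dosing. A sample that could stop dosing, for example on Day 10, would need an added venipuncture and is not part of this fix.

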#### 5.2.4 Electrocardiogram

Twelve-lead ECGs (I, II, III, aVR, aVL, aVF, V1 - V6) will be recorded using a computerised electrocardiograph (CardioSoft EKG System, at the times provided in the Flow Chart.

c41232811-04 Trial Protocol Page 46 of 84

Proprietary confidential information © 2023 Boehringer Ingelheim International GmbH or one or more of its affiliated companies

To achieve a stable heart rate at rest and to assure high quality recordings, the site personnel will be instructed to assure a relaxed and quiet environment, so that all subjects are at complete rest.

All ECGs will be recorded for a 10 sec duration after subjects have rested for at least 5 min in a supine position. ECG assessment will always precede all other trial procedures scheduled for the same time to avoid compromising ECG quality.

All ECGs will be stored electronically on the Muse CV Cardiology System (
. Electrode placement will be performed according to the method of Wilson, Goldberger and Einthoven.

All locally printed ECGs will be evaluated by the investigator or a designee. Abnormal findings will be reported as AEs (during the trial) or baseline conditions (if identified at the screening visit) if assessed to be clinically relevant by the investigator. Any ECG abnormalities will be carefully monitored and, if necessary, the subject will be removed from the trial and will receive the appropriate medical treatment.

ECGs may be repeated for quality reasons (for instance, due to alternating current artefacts, muscle movements, or electrode dislocation) and the repeated ECG will be used for analysis. Additional (unscheduled) ECGs may be collected by the investigator for safety reasons.

#### 5.2.5 Other safety parameters

#### 5.2.5.1 Suicidality assessment

The C-SSRS is a semi-structured, investigator-rated interview, developed by clinical experts in cooperation with the FDA, assessing both suicidal behaviour and suicidal ideation. It does not give a global score, but provides some categorical and some severity information specifically for behaviour and ideation [R08-1147].

The C-SSRS interview may be administered by a physician or a study nurse with C-SSRS training. It has a typical duration of five minutes, and causes only a low burden on subjects. At a minimum, the interview consists of 2 screening questions related to suicidal ideation and 4 related to suicidal behaviour, and may be expanded to up to 17 items in case of positive responses. Free text entries are allowed.

The C-SSRS has been widely used in large multinational CTs. The C-SSRS will be administered at the screening visit (using the 'screening / baseline' version) with the aim to exclude subjects with active moderate or severe symptomatology within a specified time prior to the screening or baseline visit. The life time history of suicidal ideation and behaviour will also be recorded. See Section 10.1 for the original English C-SSRS. For this trial, the paper version of the respective German translation will be used. After the screening visit, the 'since last visit' version is used for the suicidality assessment at the time points indicated in the Flow Chart.

**Positive** reports are generated for any of the following findings:

#### Suicidal ideation

• Suicidal ideation with intention to act (type 4)

**Boehringer Ingelheim** BI Trial No.: 1402-0019 c41232811-04

**Trial Protocol** 

Page 47 of 84 Proprietary confidential information © 2023 Boehringer Ingelheim International GmbH or one or more of its affiliated companies

Suicidal ideation with specific plan and intent (type 5)

#### Suicidal behavior

- Completed suicide
- Suicide attempt
- Interrupted attempt
- Aborted attempt
- Preparatory actions toward imminent suicidal behaviors.

Negative reports of suicidal ideation are defined as reports when there are no indications of the above, i.e. suicidal ideation of type 1-3.

The investigator is to review positive and negative reports for plausibility and clinical relevance. Doubtful reports may be repeated or reports may be validated by a consulting psychiatrist.

If there is a confirmed positive report of suicidal behaviour or suicidal ideation type 4 or 5 after start of trial, the investigator is to immediately interview the subject during the clinic visit, and/or is to consult a psychiatrist. If the positive report is confirmed, appropriate actions for the subject's safety have to be initiated.

For details regarding AE reporting see section 5.2.6.2.4

#### 5.2.6 Assessment of adverse events

#### 5.2.6.1 Definitions of adverse events

#### 5.2.6.1.1 Adverse event

An adverse event (AE) is defined as any untoward medical occurrence in a patient or clinical investigation subject administered a medicinal product and which does not necessarily have to have a causal relationship with this treatment.

An AE can therefore be any unfavourable and unintended sign (including an abnormal laboratory finding), symptom, or disease temporally associated with the use of a medicinal product, whether considered related or not.

The following should also be recorded as an AE in the CRF and BI SAE form (if applicable):

- Worsening of the underlying disease or of other pre-existing conditions
- Changes in vital signs, ECG, physical examination, and laboratory test results, if they are judged clinically relevant by the investigator

If such abnormalities already pre-exist prior to trial inclusion, they will be considered as baseline conditions and should be collected in the eCRF only.

#### 5.2.6.1.2 Serious adverse event

A serious adverse event (SAE) is defined as any AE which fulfils at least one of the following criteria:

- Results in death
- Is life-threatening, which refers to an event in which the patient was at risk of death at the time of the event; it does not refer to an event that hypothetically might have caused death if more severe
- Requires inpatient hospitalisation, or prolongation of existing hospitalisation
- Results in persistent or significant disability or incapacity
- Is a congenital anomaly/birth defect
- Is deemed serious for any other reason if it is an important medical event when based upon appropriate medical judgment which may jeopardise the patient and may require medical or surgical intervention to prevent one of the other outcomes listed in the above definitions. Examples of such events are intensive treatment in an emergency room or at home for allergic bronchospasm, blood dyscrasias or convulsions that do not result in hospitalisation or development of dependency or abuse

